10.8.2 LABORATORY DATA

Baseline results, worst post baseline values (minimum or maximum value as determined by the specific analyte), change from baseline to worst post baseline values for hematology and serum chemistry collected by local laboratories, will be summarized using descriptive statistics, by study part, cohort and overall, in the safety population. Hematology will include Hemoglobin, Hematocrit,

, Platelet count, and White blood cell count with differential. Serum chemistry will include Albumin, Alanine aminotransferase, Alkaline phosphatase, Aspartate aminotransferase, Blood urea nitrogen or Urea, Bicarbonate, Creatinine, Creatine kinase, Electrolytes (Na, K, Cl, Ca, P, Mg), Glucose, Lactate dehydrogenase, Total bilirubin, Total protein, and Uric acid.

Results of coagulation tests (prothrombin time, international normalized ratio, activated partial thromboplastin time), urine analysis data will be summarized at each scheduled visit. Actual laboratory values, and changes from baseline in laboratory values, will be summarized in SI units using descriptive statistics, by study part, dose group, cohort and overall, in the safety population.

For coagulation tests, descriptive statistics will include CV%, geometric mean and geometric SD, calculated as: geometric SD = $\exp(\text{SQRT}(v))$ where v is the squared standard deviation of the log-transformed values.

Shift tables classified by CTCAE grades (grade 0, grade 1, grade 2, grade 3, grade 4, grade 5) from baseline to worst post-baseline grade per cohort, may be presented by selected laboratory tests, where applicable. For laboratory tests for which grades of severity are not defined by CTCAE, results will be graded by the low/normal/high classifications based on laboratory normal ranges.

Urinalysis and microscopic analysis of the urine will be presented in a listing.

For laboratory results reported with a prefix, i.e., "<", "<=", "=>" or ">", the value derived from reported results without a prefix will be analyzed.

Change from baseline scatter plot for selected laboratory analytes will be provided.

Data listings will be produced for all collected laboratory data, including pregnancy test results.

10.8.3 VITAL SIGNS

Vital signs assessments (body temperature, pulse, systolic and diastolic blood pressure) and weight will be tabulated by visit.

Baseline results, change from baseline results of vital signs (systolic and diastolic blood pressure [mmHg], pulse [beats per minute]), temperature [degree C]) signs will be summarized by study part, by cohort (by dose level in Part A and by cancer type in Part B) using descriptive statistics.

In addition, number and percentages of patients by categories (abnormal low, normal, abnormal high) by visit and overall will be calculated and summarized for each of Part A and Part B.

Data listings will be produced for all collected vital sign data.

10.8.4 ELECTROCARDIOGRAM

ECG results will be summarized by study part, by cohort (by dose level in Part A and by cancer type in Part B) and scheduled visit. QTc interval in msec (Fredericia) will be summarized using descriptive statistics and ECG interpretation will be summarized by number and percentage.

ECG interpretation will be tabulated by a shift table (baseline vs. worst post baseline observation including unscheduled visits).

QTcF will be categorized using the FDA guidance thresholds as follows: > 450 msec, > 480 msec and > 500 msec. Frequency and proportion of patients that exceed the FDA guidance thresholds will be summarized by visit and overall, for Part A and Part B. Frequency and proportion of patients with increase from baseline of more than 30 msec and more than 60 msec will be summarized by visit and overall for Part A and Part B.

10.8.5 OTHER SAFETY PARAMETERS

ECOG categories will be tabulated by visit and a shift table (baseline vs. worst post baseline observation including unscheduled visits).

Physical examination results (normal/abnormal-not clinically significant/abnormal-clinically significant/not evaluable/not done) will be listed and a shift table (baseline vs. worst post baseline observation, including unscheduled visits) will be displayed for each body system.

Ophthalmological examination categories will be listed by study part, by cohort (by dose level in Part A and by cancer type in Part B) and scheduled visit.

11. DEVIATIONS FROM ANALYSIS AS DESCRIBED IN THE PROTOCOL

In the section §14.2 of the protocol the safety population is defined as all enrolled patients who receive at least 1 dose of study drug. The population used for analysis of clinical activity is defined as all enrolled patients who received at least one dose of study drug and had at least one follow-up tumor assessment scan, but it was not clearly stated this is the efficacy population. We clearly defined it in section §8 of the SAP.

The DOR is defined in section 14.3 of the protocol as the time from date of confirmed PR or CR to date of progression, but as we are applying a censoring rule to patients who are alive at the time of the analysis, we updated the definition in section 9.7.1 of the SAP to time from date of confirmed PR or CR to date of progression or death (from any cause).

OBI-999 2.0 mg/kg was planned to be administered in Part A but this dose was not administered to any subjects in Part A due to the toxicity observed with the 1.6 mg/kg dose. For this reason, this cohort will not be presented.

Efficacy endpoints will be analyzed in the safety and efficacy populations, because the definition of the efficacy population specifies that patients must have at least one follow-up assessment scan and so is closer to a per protocol population.

DLTs will not be derived and will be presented as collected on the eCRF. The following DLTs have been updated:

- “≥ Grade 3 fatigue, nausea and vomiting or diarrhea that does not resolve to Grade 1 or Baseline within 72 hours despite optimal supportive care” has been revised to “≥ Grade 3 fatigue, nausea and vomiting or diarrhea for more than 72 hours despite optimal supportive care”.
- “Any other Grade 3 or Grade 4 non-hematological toxicity (except Grade 3 fatigue, nausea, vomiting, or diarrhea lasting < 24 hours with optimal therapy, Grade 3 non-hematologic laboratory abnormalities that resolve to Grade 1 or baseline within 14 days)” has been

revised to. Any \geq Grade 3 non-hematological toxicity (except Grade 3 fatigue, nausea, vomiting, or diarrhea lasting < 24 hours with optimal therapy, Grade 3 non-hematologic laboratory abnormalities that resolve to Grade 1 or baseline within 14 days)".

On 10 November 2023, Sponsor stated they stop the OBI-999-001 study and elected to generate an aCSR. Therefore, as per sponsor decision, the planned analyses have been changed to:

- In section §10.5, the protocol deviations will neither be summarized nor listed.
- In section §10.6.1, the baseline and demographic characteristics will be summarized using only the safety population and listed.
- In section §10.6.2, the medical history and current medical conditions will neither be summarized nor listed.
- In section §10.6.3, the prior and concomitant medications will neither be summarized nor listed.
- In section §10.6.4, the cancer history will be summarized using only the safety population and listed.
- In section §10.6.5, other medical history will not be listed.
- In section §10.6.6, prior cancer surgeries will neither be summarized nor listed.
- In section §10.6.7, prior cancer radiotherapy will neither be summarized nor listed.
- In section §10.6.8, prior cancer medication therapy will neither be summarized nor listed.
- In section §10.6.9, smoking history will neither be summarized nor listed.
- In section §10.7.1, adverse events that will be analyzed and listed have been marked with asterisks. Only ORR analysis using safety population and ADA analysis using safety and PK populations have been selected as CBR, DOR and PFS analyses will no longer be conducted for the aCSR. Only waterfall plot (bar plot) showing the best reduction in target lesion therapy will be presented for Cohort-Expansion patients.
- In section §10.8.1, only extent of exposure will be summarized, and all study drug administration data will be listed.
- In section §10.8.2, laboratory data will only be listed. OBI decided not to conduct normalization of local laboratory assessments; therefore, data will be listed as recorded.
- In section §10.8.3, vital signs data will only be listed.
- In section §10.8.4, electrocardiogram data will only be listed.
- In section §10.8.5, ECOG, physical examination and ophthalmological data will neither be summarized nor listed.

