#### 4.4 Clinical Risks/Benefits of OBI-999

OBI-999 is an ADC composed of a humanized monoclonal IgG1 antibody conjugated with MMAE. Toxicities may include myelosuppression and neuropathy as these side effects have been observed with other ADCs based on the MMAE molecule. A complete discussion of guidance for the investigator is provided in the OBI-999 Investigator Brochure.

The risk-to-benefit ratio for this study is considered acceptable based upon the patient population, the available limited treatment options for patients with advanced solid tumors, the toxicology results and activity data observed in the preclinical safety studies, and the results of the Dose Escalation Phase of this study.

As of 02 June 2020, 13 out of 15 patients enrolled in Part A had an investigator driven tumor response assessment. The best overall response per Response Evaluation Criteria in Solid Tumors version 1.1 (RECIST 1.1) criteria was stable disease, which was observed in 5 patients, including 1 patient from Cohort 1 (0.4 mg/kg with rectal cancer), 2 patients from Cohort 2 (0.8 mg/kg; 1 with pancreatic cancer and 1 with esophageal cancer), and 2 patients from Cohort 3 (1.2 mg/kg; 1 with head and neck cancer and 1 with cancer of the appendix). However, due to the limited sample size in Part A (Dose-Escalation), a relationship between Globo H expression level and depth of clinical activity at the Recommended Phase 2 Dose (RP2D) has yet to be established in this patient population. This relationship will be further evaluated in Part B of the study at the RP2D of 1.2 mg/kg.

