#### **5.1.2 Secondary Objectives**

The secondary objectives are:

- To evaluate the preliminary clinical activity profile of OBI-999 (objective response rate [ORR], clinical benefit rate [CBR], duration of response [DOR], and progression-free survival [PFS]).
- To evaluate the immunogenicity of OBI-999 (anti-drug antibodies [ADAs]).
- To determine the serum PK of OBI-999 and its active metabolite MMAE.

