### **5.2.2 Part B – Expansion Cohort**

#### **5.2.2.1 Primary Endpoints**

- Percentage of patients with objective response, clinical benefit, DOR and PFS according to RECIST 1.1.
- Percentage of patients with ADAs in blood.

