5.4 INTERIM ANALYSIS

There will not be any other formal interim analyses except for the one related to Simon's two stage design described below; however, a description of the Dose-Escalation Phase and the selection of the RP2D may be written up for the purposes of a manuscript.

Moreover, the cohort expansion portion of the study (Part B) will enrol up to 57 patients based on Simon's two-stage design. The first stage will recruit up to 9 patients in each of three cohorts. If at least one objective response is observed, a second stage recruitment will occur with up to 10 additional patients enrolled into that cohort, for a total of up to 19 patients per cohort. If at least 4 objective responses are observed in the 19 patients, then OBI-999 will be considered worthy of further evaluation in that indication. Patients will be followed up to the 24-week scheduled response assessment for the purposes of counting objective responses for Simon's two-stage design success criteria. A formal analysis will be performed to support it.

Patient enrolment, patient disposition, baseline characteristics, cancer history, clinical benefit rate, exposure to OBI-999, AE and ECG summaries (all described in this document) will support this formal analysis at end of stage 1.

If Simon's two-stage design success criteria is not met, then the second stage recruitment will not occur, and analyses will be done for supporting an aCSR.

The description above represents the initial interim analysis planning based on the protocol. In reality at the end of the first stage of Part B, four patients did not have a RECIST post-baseline assessment and so it has been decided to replace them to have enough data to perform the go/no-go analysis. 2 'replacement' patients have been enrolled in the pancreatic cohort, while searching for 2 'replacement' patients in the colorectal cohort was in progress. On 10th November 2023, Sponsor stated they stop the study and elected to generate an aCSR and so formal go/no-go analysis never happened.

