8. ANALYSIS ENDPOINTS

Analysis endpoints are listed as per protocol. Only those endpoints marked with * will be analyzed in aCSR as per sponsor decision. Exploratory analyses are to be conducted by OBI Transnational Biology (or their designee) and may be included as appendices in the aCSR.

8.1 PRIMARY ENDPOINTS:

Part A (Dose-Escalation):

- AEs/ SAEs and laboratory abnormalities as graded by National Cancer Institute Common Terminology Criteria for Adverse Events (NCI CTCAE) version 5.0*.
- DLTs with OBI-999*.
- MTD and RP2D of OBI-999.

Part B (Cohort-Expansion):

- Percentage of patients with objective response*, clinical benefit, DOR and PFS according to Response Evaluation Criteria in Solid Tumors (RECIST) 1.1.
- Percentage of patients with ADAs in blood*.

8.2 SECONDARY ENDPOINTS:

Part A (Dose-Escalation):

- PK parameters of OBI-999 and its active metabolite MMAE*.

Part B (Cohort-Expansion):

- AEs/SAEs and laboratory abnormalities as graded by NCI CTCAE version 5.0*.
- PK parameters of OBI-999 and its active metabolite MMAE*.

8.3 EXPLORATORY ENDPOINTS:

Part A (Dose-Escalation):

- Potential predictive biomarkers for OBI-999 activity such as expression of Globo H and other tumor-associated glycans or tumor molecular phenotypes.

Part B (Cohort-Expansion):

- Potential predictive biomarkers for OBI-999 activity such as expression of Globo H and other tumor-associated glycans or tumor molecular phenotypes.

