Clinical benefit rate (CBR) is defined as the percentage of patients with confirmed CR, PR, or SD among all the patients of the safety and efficacy populations. A confirmed response will be defined as two or more consecutive assessments separated by at least 3 weeks. Patients who discontinue prior to post-baseline tumor assessments will be considered as non-responders and retained in the denominator. This analysis is similar to ORR.

If the BOR used for CBR based on unconfirmed and confirmed overall responses differs by 10%, then we will present the same summary for CBR based on unconfirmed overall responses as a sensitivity analysis.

C. Duration of Response

DOOR is defined as the time from date of confirmed PR or CR to date of progression or death due to any cause and will be expressed in months. For patients who are alive and progression-free at the time of analysis, DOOR will be censored at the last tumor assessment date. The DOOR will only be evaluated for the subgroup of patients with a confirmed PR/CR using the Kaplan Meier method.

A summary of the patients with disease progression, or death, or the number of patients censored will be presented by the median time, Q1, Q3 and survival rates along with 95% CI, minimum and maximum will be provided.

Patients who discontinue from the study without experiencing any pre-defined events or patients who completed the study period without experiencing any pre-defined events will be included in statistical analysis as censored.

Sample code for duration of response is provided below:

```
ods output Quartiles=QUARTS;
proc lifetest data=DATA method=km OUTSURV=KMEST;
by COHORT;
time AVAL*CENSOR(1);
run;
ods output close;
```

D. Progression Free Survival

PFS is defined as the time from first dose of study drug until radiographically determined disease progression or death due to any cause, whichever occurs first. Patients who are still alive or who have no progressive disease reported at analysis will be censored at the last evaluable tumor assessment date.

Patients who discontinue from the study without experiencing any pre-defined events or patients who completed the study period without experiencing any pre-defined events will be included in

the statistical analysis as censored.

A summary of the patients with progression, or death, or the number of patients censored, presenting the median time, Q1, Q3 and survival rates along with 95% CI, minimum and maximum will be provided.

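### SAP 2.0 drops three of the five named Part B primary endpoints (CBR, DOR, PFS) after the open-label study stopped, without saying why these three or what results had been seen

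*SAP*

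**What the plan says.** Protocol 5.2.2.1 gives two bullets of Part B primary endpoints: "Percentage of patients with objective response, clinical benefit, DOR and PFS according to RECIST 1.1" and "Percentage of patients with ADAs in blood". The four activity measures also appear in Protocol 5.1.2, but under secondary objectives, so their rank is not consistent within the protocol.

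SAP 8.1 repeats the list with an asterisk on the parts that the aCSR will analyze: "Percentage of patients with objective response*, clinical benefit, DOR and PFS according to Response Evaluation Criteria in Solid Tumors". Among the activity endpoints only objective response carries the mark; ADA is also marked. SAP 11 confirms the consequence: "CBR, DOR and PFS analyses will no longer be conducted for the aCSR". The reason recorded there, in SAP 8 and in the revision history is the sponsor's decision of 10 November 2023 to stop the study and write an abbreviated report. Protocol 14 lets the SAP override the protocol where they differ, so the removal governs.

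CBR also had a role in the planned stage 1 decision. SAP 5.4 says that "clinical benefit rate, exposure to OBI-999, AE and ECG summaries (all described in this document) will support this formal analysis". The same section records that the go/no-go analysis was never carried out.

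SAP 10.7.1 still holds definitions for all three dropped endpoints, and Kaplan-Meier sample code for DOR. Its PFS paragraph contains this censoring rule: "Patients who are still alive or who have no progressive disease reported at analysis will be censored at the last evaluable tumor" assessment date.

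**The concern.** Prespecified endpoints were removed late, in a study where nobody was blinded (SAP 6) and where the sponsor already knew which stage 1 patients lacked a post-baseline scan (SAP 5.4). A reader of the report will see one activity endpoint out of four and cannot tell whether the choice was independent of the results.

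The dropped measures could also matter for interpretation. Protocol 4.4 reports that the best response in Part A "was stable disease, which was observed in 5 patients", among 13 assessed. That is an interim snapshot at 02 June 2020. If Part B looked similar, response rate alone would say little, and disease control and time to progression would hold much of the remaining activity information.

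**Working it through.** **1. The plan's own figure.** The design rests on objective response alone: 9 then 19 patients per cohort, continue with at least 1 response, succeed with at least 4 (Protocol 14.1). Probability of success at true rate p is the sum over x ≥ 1 of P(X1 = x | 9, p) × P(X2 ≥ 4 − x | 10, p).
- p = 25%: 0.7201, which reproduces the stated 72% power.
- p = 10%: 0.1100, within the stated one-sided 0.12 if that is read as a ceiling.

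Restoring the other endpoints therefore changes no sample size.

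**2. Count.** Five endpoints are named and two kept (objective response, ADA). Three are dropped: 3/5 = 60%.

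**3. Timing.** SAP 1.0 is dated 21 April 2023, the stop 10 November 2023 and SAP 2.0 12 July 2024. Stop to SAP 2.0 is 245 days; 245/30.4 = 8.1 months.

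**4. What survives.** The starred objective-response part of SAP 10.7.1 includes counts by best-overall-response category and a by-visit response listing. SAP 11 keeps the waterfall plot as the only activity figure, so the swim lane plot goes.

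| Dropped | What can still be recovered | What is lost |
|---|---|---|
| CBR | CR, PR and SD counts | Confirmed SD, the rate and its interval |
| PFS | Partial reconstruction from the listing | Kaplan-Meier summary, median, event counts |
| DOR | Nothing to recover without a confirmed response | A summary, only if a response is confirmed |

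The SD count is not CBR. Best response of SD needs one qualifying assessment at 6 weeks or later. CBR as written needs confirmation: two consecutive assessments at least 3 weeks apart. With scans every 6 weeks in the first 3 months, a patient stable at week 6 and progressing at week 12 counts as SD in the table but not toward CBR.

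**5. When DOR has data.** The chance of at least one response among n patients is 1 − (1 − p)^n.
- n = 9: 1 − 0.9^9 = 61.3% at 10%; 1 − 0.75^9 = 92.5% at 25%.
- n = 11 (assuming 9 plus the 2 pancreatic replacements): 68.6% and 95.8%.

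**6. The PFS censoring sentence.** The event is progression or death. Its complement is alive and not progressed. The sentence joins the two conditions with an or. Compared literally:

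| Patient | Event definition | Censoring sentence |
|---|---|---|
| Alive, no progression | Censored | Censored |
| Alive, progressed | Event | Censored |
| Dead, no progression reported | Event | Censored |
| Dead, progressed | Event | Event |

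Two of the four rows conflict. Protocol 14.3 has the same wording.

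**7. Precision.** Restored estimates would be rough. For illustration, 3/9 with clinical benefit has a Clopper-Pearson 95% interval of 7.5% to 70.1%.

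**The case against.** The strongest reply is that this is an ordinary abbreviated report after early termination. The cut runs across the plan: protocol deviations, medical history, medications and ECOG status are dropped, while laboratory, vital-sign and ECG data are only listed. The activity endpoint kept is the one that sized the study. If the dropped endpoints were the likelier ones to show activity, the sponsor kept the less flattering one. SAP 11 already discloses that the changes followed the stop, and CBR's role at stage 1 lapsed with the go/no-go analysis. The primary label is itself unsettled, since the same measures are secondary objectives. All of this stands. It does not explain why these three were chosen, and the measures were prespecified under either label.

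Four stronger readings are tempting and are not supported.
- **A reader might infer that the sponsor chose endpoints according to the results.** No text says so. The dates and open-label design make access possible; they do not show use.
- **A reader might infer that only response rate and ADA will be reported.** That is true of the Part B primary endpoints only. Best-response counts, the response listing, the waterfall plot, adverse events, PK and exposure remain.
- **A reader might infer that zero responses in a cohort would leave the 25% rate open,** because the two-sided 95% upper limit is 33.6% for 0/9 and 28.5% for 0/11. At the design's own one-sided 0.12 level the upper limit is 1 − 0.12^(1/n): 21.0% for 0/9 and 17.5% for 0/11. Both exclude 25%.
- **A reader might infer from Part A that Part B has no responses.** The Part A figure covers 13 assessed of 15 enrolled at that date, while SAP 5.1.1 gives 22 enrolled in all. Those patients were not selected for Globo H and spanned several doses.

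On the censoring sentence, the next paragraph of SAP 10.7.1 censors patients who had no defined event, so the intended meaning is recoverable. The wording still conflicts with the definition just before it.

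**Conclusion.** The point holds in a limited form. Three of five named Part B primary endpoints are removed in a SAP dated 245 days after an open-label study was stopped. The removal is disclosed with an operational reason, but with no reason for this particular selection and no statement of what had been seen. Selective reporting is not shown and cannot be ruled out.

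The substantive loss is the PFS summary and CBR as defined. DOR is a loss only where a response is confirmed.

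This rests on two readings: that the starred objective-response part keeps its best-response table and by-visit listing, and that confirmation in the CBR definition applies to stable disease. If confirmation were meant for CR and PR only, CBR could be nearly read off the retained table and PFS would be the main loss. The figure of about 9 patients per cohort assumes that stage 1 filled as planned.

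**What to change.** - In SAP 8.1, 10.7.1 and 11, mark and report CBR and PFS by cohort and for the Cohort-Expansion Total in the safety population. Give CBR its own derivation of confirmed stable disease.
- List DOR for any confirmed responder.
- Reword the PFS censoring sentence so that only patients who are both alive and without progressive disease are censored.
- Add to SAP 11 why CBR, DOR and PFS were dropped and which response or progression data had been seen by then.
- Where the report cites the Part A stable-disease figure, label it as an interim snapshot at 02 June 2020.

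The cost is small: one extra derivation and one Kaplan-Meier table, with definitions and Kaplan-Meier sample code already in SAP 10.7.1. No sample size changes. The downside is imprecise estimates that need to be presented as descriptive.

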4. STUDY OBJECTIVES

4.1 PRIMARY OBJECTIVES

The primary objectives are:

- To determine the safety and tolerability of OBI-999 when administered intravenously (IV) to patients with advanced solid tumors.
- To determine the maximum tolerated dose (MTD) and recommended phase 2 dose (RP2D) of OBI-999.

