5.3 SAFETY REVIEW COMMITTEE

The safety review committee (SRC) for this study will be comprised of the clinical lead, medical monitor, and the Investigator(s) or designee. The SRC will act in an advisory capacity to monitor

patient safety and efficacy during the trial and its activities will be defined in a separate SRC charter.

This SRC convened after each cohort completed the first cycle of treatment during Part A (Dose-Escalation), to review safety data (AEs and laboratory toxicities) and to determine whether DLTs occurred.

The RP2D for Part B (Cohort-Expansion) was determined by the SRC based on both the frequency of DLTs observed during Cycle 1 according to the 3+3 design, and also by the frequency and severity of cumulative toxicities such as peripheral neuropathy. The SRC will continue to monitor the severity and frequency of acute and cumulative toxicities at regular intervals, i.e., every 3 months, to ensure acceptable tolerability of the selected RP2D and of the effectiveness of dose modification rules. The SRC will receive updated tabulations of recruitment, AEs, SAEs, clinical laboratory events, and dose modifications which will serve as the basis for their assessments.

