10.7.1 PRIMARY ENDPOINTS

PART A (DOSE-ESCALATION)

A. AEs/ SAEs and laboratory abnormalities as graded by NCI CTCAE version 5.0*.

Treatment emergent adverse events (TEAEs) are defined as AEs with onset dates on or after the start of study drug until 28 days after the last dose of study drug or if it is present prior to receipt of the study treatment but worsens in severity or increases in frequency on or after the first dose. AEs having both onset and end dates missing will be considered as TEAEs.

TEAEs will be summarized by study part, cohort (by dose level in Part A and by cancer type in Part B), SOC, PT, severity grade, and relationship to treatment. SAEs, deaths, and AEs leading to early treatment discontinuation (collected on Adverse Events eCRF page) will be summarized. The summaries will be sorted by decreasing order of overall incidence of SOCs and decreasing order of overall incidence of PTs within SOCs.

Events reported as “Unrelated” or “Unlikely related” to study drug will be considered as unrelated to the study drug. Events reported as “Possibly related”, “Probably related”, “Definitely related” to study drug or without relationship information will be considered as related to the respective treatment.

Overview summaries of the number and percentages of patients and number of events within the following categories will be provided by study part and by cohort (by dose level in Part A and by cancer type in Part B):

- Any TEAE
- Any TEAE grade ≥ 3
- Any TEAE related to OBI-999
- Any Serious TEAE
- Any Non-Serious TEAE
- Any Serious TEAE related to OBI-999
- Any TEAE leading to death
- Any TEAE leading to discontinuation of OBI-999 (defined as AE with an action taken equals to “Drug Withdrawn”)
- Any Serious TEAE leading to discontinuation of OBI-999 (defined as AE with an action taken equals to “Drug Withdrawn”)
- Any TEAE leading to study discontinuation (defined as AE flagged as Grade 4 infusion reactions and OBI-999 related toxicity, or intercurrent illness in the “End of Study” eCRF

page)

- Any Serious TEAE leading to study discontinuation (defined as AE flagged as Grade 4 infusion reactions and OBI-999 related toxicity, or intercurrent illness in the “End of Study” eCRF page)

Tables by SOC and PT will be displayed for following AEs. Only those AEs marked with * will be analyzed in the aCSR as per sponsor decision.

- TEAEs*
- TEAEs grade ≥ 3 *
- TEAEs related to OBI-999*
- Serious TEAEs*
- Non-Serious TEAEs

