10.8.1 EXPOSURE TO STUDY TREATMENT AND TREATMENT COMPLIANCE

The number of doses received, number of doses adjusted along with reasons of dose adjustment, total actual dose received in mg, total planned dose in mg, percentage of compliance (defined below), number of infusions interrupted along with reasons for infusion interruptions; number of infusions prematurely discontinued along with reasons for infusion prematurely discontinued, and the extent of exposure (calculated as last dose date – first dose date +1), will be summarized using descriptive statistics by study part, cohort, and overall.

Percentage of compliance for a patient will be defined as the total actual dose received divided by the total planned dose multiplied by 100.

$$\text{Percentage of compliance (\%)} = \frac{\text{Total actual dose received in mg}}{\text{Total planned dose in mg}} \times 100$$

Extent of exposure will also be summarized categorically by number and percentages for each of the following categories and cumulatively according to these categories:

- > 0 and ≤ 3 weeks
- > 3 and ≤ 6 weeks
- > 9 and ≤ 12 weeks
- > 12 and ≤ 18 weeks
- > 18 and ≤ 24 weeks
- > 24 and ≤ 36 weeks
- > 36 and ≤ 48 weeks
- > 48 weeks

In addition, the percentages of compliance will be presented by the specific ranges for each study part and cohort:

- < 80%
- ≥ 80% to < 120%
- ≥ 120%

Data listings will be produced for all study drug administration data.

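### After SAP 11 the abbreviated report lists dose reductions, skipped doses and interrupted infusions but summarizes none of them, and extent of exposure cannot stand in for them

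*SAP*

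**What the plan says.** SAP 4.1 gives as its first primary objective: "To determine the safety and tolerability of OBI-999 when administered intravenously (IV) to patients with advanced solid tumors".

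SAP 10.8.1 planned a descriptive exposure summary by study part and cohort. It begins "The number of doses received, number of doses adjusted along with reasons of dose adjustment, total actual dose received in mg" and goes on to planned dose, percentage of compliance, infusions interrupted or stopped early (each with reasons), and extent of exposure.

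SAP 11, which sets out the cuts made after the sponsor stopped the study on 10 November 2023, says: "In section §10.8.1, only extent of exposure will be summarized, and all study drug administration data will be listed".

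SAP 10.7.1 lists 11 TEAE overview rows and the same 11 categories for tables by system organ class and preferred term. The categories defined by what was done with the drug are "Any TEAE leading to discontinuation of OBI-999" and its serious counterpart, both identified by an action taken of drug withdrawn.

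**The concern.** In this protocol, dose modification is a main response to toxicity short of withdrawal. Protocol Table 8-1 provides for a hold and then a reduced dose after Grade 2 and after Grade 3 toxicity, and Protocol 8.3.2.1 does the same for peripheral neuropathy. How often that happened, and how much of the planned dose patients received, is part of describing tolerability at the recommended Phase 2 dose (RP2D).

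The item that answers this directly, "number of doses adjusted along with reasons of dose adjustment", was in the plan and is no longer to be summarized. A reader of the abbreviated report could see how long patients stayed on treatment and how many withdrew. To learn how many were reduced, held or interrupted, the reader would have to count through listings.

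**Working it through.** The plan states no figure to reproduce. The check compares the sections and then applies the SAP's own exposure formula.

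**1. What survives from SAP 10.8.1**

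| Item planned in 10.8.1 | After SAP 11 |
|---|---|
| Number of doses received | listing only |
| Doses adjusted, with reasons | listing only |
| Actual and planned dose, compliance | dosing data listed; no summary |
| Infusions interrupted or stopped early, with reasons | listing only |
| Extent of exposure | summarized |

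**2. Whether the TEAE tables fill the gap.** The 11 overview rows are: any; Grade 3 or higher; related; serious; non-serious; serious related; fatal; drug discontinuation and its serious subset; study discontinuation and its serious subset. None is for reduction, hold or skip. Of the 11 tables by organ class and term, 10 are starred for the abbreviated report (all but non-serious), and none of them covers it either. The worst-grade tables count Grade 2 events but do not say what happened to the dose.

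**3. Whether deviations fill the gap.** They do not. SAP 11 neither summarizes nor lists protocol deviations, apart from dosing and sampling deviations in the separate pharmacokinetic plan. Under Protocol 8.3, a medically justified dose skipped for safety is not recorded as a deviation.

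**4. Whether extent of exposure can substitute.** The formula in 10.8.1 is last dose date − first dose date + 1. Inputs: 21-day cycles, first dose on Cycle 1 Day 1, last dose on Cycle 6 Day 1.

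Extent = 5 × 21 + 1 = 106 days (106 / 7 = 15.1 weeks).

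The four patterns below are assumed. They use the 75% figure in Table 8-1 and the rule that a dose outside the ±3-day window is skipped. Planned dose is taken as six full doses.

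| Pattern | Doses given | Share of planned dose | Extent |
|---|---|---|---|
| Six full doses | 6 | 6 / 6 = 100% | 106 days |
| 75% from dose 2 onward | 6 | (1 + 5 × 0.75) / 6 = 79% | 106 days |
| Cycles 2 and 3 skipped, otherwise full | 4 | 4 / 6 = 67% | 106 days |
| Cycles 2 and 3 skipped, then 75% | 4 | (1 + 3 × 0.75) / 6 = 54% | 106 days |

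The retained summary is the same in all four rows. The dropped compliance bands in 10.8.1 (below 80%, 80% to below 120%, 120% or more) would put the first pattern in the middle band and the other three in the lowest.

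**5. A side observation on the retained measure.** Its categories go from over 3 to 6 weeks straight to over 9 to 12 weeks. Three on-schedule doses give 2 × 21 + 1 = 43 days, or 6.14 weeks, which fits no category.

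**The case against.** The case for leaving SAP 11 alone has substance. The study was stopped, an abbreviated report is a legitimate choice, and the cuts are declared openly. The RP2D had already been set, the formal go/no-go analysis never took place, and adverse events in Part B are formally a secondary endpoint. Protocol 14.5 requires tabulation of serious events and events causing discontinuation, both of which are kept; it does not promise a table of events leading to reduction or hold. The numbers are small (22 patients in Part A, up to 9 per cohort in stage 1 of Part B), so listings can be read by hand. All of this stands, and it limits how much weight the point carries.

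Three stronger readings are tempting, and the documents do not support them.

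- A reader might infer that tolerability will be judged on discontinuations alone. It will not. All, Grade 3 or higher, related, serious and fatal TEAEs, worst grade and dose-limiting toxicities remain tabulated.
- A reader might infer that the dosing data are withheld. They are not. Administration data are listed, the listing of all TEAEs is kept, and Protocol 14.5 includes action taken with study drug in the adverse event listing.
- A reader might infer that the Safety Review Committee cannot do its task "to ensure acceptable tolerability of the selected RP2D and of the effectiveness of dose modification rules". SAP 5.3 gives the committee its own tabulations of dose modifications during the trial, separate from the report. The section does show that the plan itself connects dose modification with RP2D tolerability.

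What remains after these concessions is narrow. A summary the SAP had already specified was removed, and what was kept cannot carry the same information.

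**Conclusion.** The point holds as a reporting gap. Under SAP 11, dose modification and delivered dose, which belong to the primary safety and tolerability objective, appear only in listings. Extent of exposure cannot reveal them: it is 106 days for received-to-planned shares from 54% to 100% in the illustration.

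The illustration rests on assumed dosing patterns and on counting planned dose as full dose in every cycle. The documents give no rates of reduction, hold or interruption and no final Part B enrolment, so the number of patients affected cannot be estimated. Nothing here suggests that a conclusion of the trial would change. This is an inexpensive improvement to the report.

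**What to change.** In SAP 11, replace the entry for 10.8.1 with one that keeps the following as summaries, by dose level in Part A and by cohort in Part B, alongside extent of exposure:

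- number of doses received;
- doses adjusted, with reasons;
- infusions interrupted, with reasons;
- percentage of compliance (total actual over total planned dose).

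State how planned dose is counted. SAP 10.8.1 does not say whether skipped cycles count or whether a reduced dose becomes the new planned dose. If both were reset, all four patterns above would show 100%.

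In SAP 10.7.1, add overview rows for TEAEs leading to dose reduction and to dose hold or skip, provided the action-taken field on the adverse event page holds those values. Protocol 12.5.1 confirms that the field is collected, but the documents show only the drug-withdrawn value, so check the form first. While 10.8.1 is open, add the missing category of over 6 to 9 weeks.

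The cost is one table and up to two rows from data already being listed, and a slightly wider abbreviated report. The planned-dose definition and the added category are text edits to the SAP. No new data collection appears to be needed.
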